11.5. Causality Assessment

An AE is not automatically related to the study device or procedure simply because the subject is wearing the device and participating in the study. The event should be reviewed to determine if the device or study procedure could have possibly caused the event and therefore is related to the study device or procedure.

Causality assessment is the determination of the relationship between an AE and the device being studied. It is expected that the investigational center will review all elements surrounding the AE to properly assess the causality of the event to the study device or to a study procedure.

This review would include the subjects' description of the event, study device uploads and medical records (if applicable) from the treating facility. These records will be made available to sponsor.

Investigators should classify the relationship between the AE and the study device or study procedures using one of the five possible causality categories listed below:

- **Not related:** relationship to the device or procedures can be excluded when:
 - \circ $\,$ the event is not a known side effect of the product category the device belongs to or of similar devices and procedures
 - the event has no temporal relationship with the use of the investigational device or the procedures;

10768467DOC Version C Page 69 of 97

- the event does not follow a known response pattern to the medical device (if the response pattern is previously known) and is biologically implausible;
- the discontinuation of medical device application or the reduction of the level of activation/exposure - when clinically feasible – and reintroduction of its use (or increase of the level of activation/exposure), do not impact on the serious event;
- the event involves a body-site or an organ not expected to be affected by the device or procedure;
- the event can be attributed to another cause (e.g. an underlying or concurrent illness/ clinical condition, an effect of another device, drug, treatment or other risk factors);
- the event does not depend on a false result given by the investigational device used for diagnosis, when applicable;
- o harms to the subject are not clearly due to use error;
- o In order to establish the non-relatedness, not all the criteria listed above might be met at the same time, depending on the type of device/procedures and the serious event.
- **Unlikely:** the relationship with the use of the device seems not relevant and/or the event can be reasonably explained by another cause, but a relationship to the device cannot be completely ruled out.
- **Possible:** the relationship with the use of the investigational device is weak. Alternative causes are also possible (e.g. an underlying or concurrent illness/ clinical condition or/and an effect of another device, drug or treatment). Cases where relatedness cannot be assessed should also be classified as possible.
- **Probable**: the relationship with the use of the investigational device seems relevant and/or the event cannot reasonably be explained by another cause.
- **Causal relationship:** the event is associated with the investigational device or with procedures beyond reasonable doubt when:
 - the event is a known side effect of the product category the device belongs to or of similar devices and procedures;
 - the event has a temporal relationship with investigational device use/application or procedures;
 - the event involves a body-site or organ that
 - the investigational device or procedures are applied to;
 - the investigational device or procedures have an effect on;
 - the event follows a known response pattern to the medical device (if the response pattern is previously known);
 - the discontinuation of medical device application (or reduction of the level of activation/exposure) and reintroduction of its use (or increase of the level of activation/exposure), impact on the event (when clinically feasible);
 - other possible causes (e.g. an underlying or concurrent illness/ clinical condition or/and an effect of another device, drug or treatment) have been adequately ruled out;

10768467DOC Version C Page 70 of 97

- harm to the subject is due to error in use;
- the event depends on a false result given by the investigational device used for diagnosis, when applicable;
- o In order to establish the relatedness, not all the criteria listed above might be met at the same time, depending on the type of device/procedures and the serious event.

Example: A severe hyperglycemia AE with the following event description would have the following causality assessment for device relatedness:			
Improved glucose without an infusion set/site change Not related			
Changed infusion set with glucose improvement	Possible		
Infusion set fell out, bent cannula, occlusion alarm Causal relationship			

11.6. Anticipated or Unanticipated

If the AE is determined to be related to the study device the sponsor will then assess the event to determine if it is anticipated or unanticipated.

- **Anticipated:** the event is identified in the CIP; labeling; report of priors/IB or user guide.
- **Unanticipated:** the event has not been previously identified in the CIP; labeling; report of priors/IB or user guide.

11.7. Skin Assessment: Glucose Sensor Insertion Sites

Skin irritation may be associated with the insertion of the device or device wear and may be associated with the adhesives and tapes used to secure the study devices. The area of skin associated with glucose sensor insertion and wear will be assessed following the removal of each glucose sensor by investigational center staff. Either subject or investigational center may remove a sensor if they are concerned with skin irritation or skin discomfort. The Investigational Center staff will complete a skin assessment each time a study sensor is removed from a subject, independent of the length of time inserted or the amount of time elapsed between sensor removal and the assessment.

It is expected that subjects will experience mild irritation, redness, bleeding or bruising associated with the insertion and or wear of the glucose sensor and devices. These events are to be documented and captured on the Skin Assessment eCRF. An AE eCRF will only be completed if the skin assessment observation meets the following criteria:

- Infection
- Any observation that meets the criteria of moderate or severe per the skin assessment case report form (for example: bruising equal to or greater than 6 cm in longest diameter; rash that requires prescription medication)

10768467DOC Version C

Subjects will not be required to return to the investigational center for examination to document resolution of Skin Assessment observations. The subject should be instructed to contact the investigational center for follow-up if there is any worsening or change that concerns the subject. Worsening should be assessed to determine if AE reporting is necessary.

12. Data Review Committees

A CEC consisting of external physicians with an expertise in endocrinology and the management of diabetes including insulin pumps and CGM will be convened. The CEC will review AEs as required per protocol, and may include reports of:

- Serious Adverse Event
- Serious Adverse Device Effect
- Unanticipated Adverse Device Effect
- Severe Hypoglycemia
- Diabetic Ketoacidosis

The CEC will assess events to determine agreement or disagreement with the investigator classification of an event. The CEC will only provide three causality assessments for device and procedure relatedness: Not Related, Possible, and Causal relationship.

Causality Categories for Investigational Center	Causality Categories for CEC:
Not Related	Not Related
 Unlikely 	 Possible
 Possible 	 Causal relationship
Probable	
 Causal relationship 	

The sponsor will notify the investigator of any disagreement in assessment of an event by the CEC.

13. Device Deficiencies and Troubleshooting

The Medtronic 24-Hour HelpLine (HL) will be consulted for device troubleshooting (e.g. assistance is needed by subject to operate their device(s)). When subjects call the HL, they are instructed to notify the

10768467DOC Version C Page 72 of 97

HL operator that they are currently participating in a clinical research study. All device deficiencies that are reported to the HL will be documented by the HL staff.

The investigational center will be provided with a copy of all HL calls for their subjects. The HL calls should be reviewed for investigational center staff awareness for the possibility of an AE. If an AE is detected the investigational center staff will complete the appropriate eCRF(s).

Any device deficiency the subject may have should be reported to the investigational center staff. A device deficiency is any inadequacy of a medical device with respect to its identity, quality, durability, reliability, safety, or performance. NOTE: Device deficiencies include malfunctions, use errors, and inadequate labeling. (**Adapted from ISO14155:2011**)

All device returns be processed by the investigational site staff.

It is the responsibility of the investigator to follow their EC reporting requirements.

Device Deficiency	Inadequacy of a medical device with respect to its identity, quality, durability, reliability, safety or performance.
	NOTE: Device deficiencies include malfunctions, use errors, and inadequate labeling.
	(ISO 14155:2011 section 3.15)
	Any unreasonable risk caused by a medical device in normal use during clinical trial that may endanger human health or life safety, such as label error, quality issues, malfunction and etc.
	(NMPA Order No.25 Article 93)

14. Statistical Design and Methods

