10.1. Potential Risks

10768467DOC Version C Page 59 of 97

Risk with Sensors	Prevention and Mitigation
Risks with Sensors may include: Skin irritation or reaction to adhesives Bruising Discomfort Redness Bleeding Excessive bleeding due to anticoagulants Pain Rash Infection Irritation from tapes used with glucosesensing products Raised bump Appearance of a small "freckle-like" dot where needle was inserted Allergic reaction Syncopal episode secondary to needle insertion Soreness or tenderness Swelling at insertion site Sensor fracture, breakage or damage Minimal blood splatter associated with sensor needle removal Residual redness associated with adhesive and/ or tapes Scarring Scab Blister Itchiness Inflammation Anxiety Incorrect sensor glucose reading results in incorrect diabetes management Subject over-treating secondary to alarms which can result in hyperglycemia or hypoglycemia Anxiety associated with insertion	Prevention and mitigation include: • Follow the provided user guides for insertions and care of sensors. • If a sensor site becomes infected or inflamed, the sensor should be removed and another placed in a new location Base diabetes management on fingerstick readings and not sensor glucose values.
Risks with Transmitter	Prevention and Mitigation
Risks with Transmitter may include: Skin irritation or reaction to adhesives Bruising Discomfort Redness Radness Pain Rash Infection Irritation from tapes used with glucosesensing products	 Prevention and mitigation include: Follow the provided user guides for transmitters. Training on proper use of the transmitters.

10768467DOC Version C Page 60 of 97

•	Raised bump	
•	Allergic reaction	
•	Soreness or tenderness	
•	Residual redness associated with adhesive	
	and/ or tapes	
•	Scarring	
•	Scab	
•	Blister	
	w	

ScabBlisterItchinessInflammation		
Risks with Serter	Prevention and Mitigation	
Risks with Serters may include: • Improper insertion may lead to device performance issue or hyperglycemia	Prevention and mitigation include: • Follow the provided user guides for insertions and care of Serters. • Training on proper use of the Serter and skin preparation prior to insertion.	
Risks with Finger Sticks	Prevention and Mitigation	

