14.3. Sensor Disposition

The number of Guardian[™] Sensor (3) insertions and Guardian[™] Sensor (3) removals for every subject enrolled in the study will be presented.

A descriptive analysis of Guardian[™] Sensor (3) disposition including Guardian[™] Sensor (3) dislodgement and reasons why it dislodged will be included in the Final Report. Guardian[™] Sensor (3) insertion and removals will be characterized by the following:

- Duration of Guardian™ Sensor (3) wear by investigational center subject report
- The number and percentage of Guardian™ Sensor (3)s remaining in place at study end
- Reason for removal: for example, scheduled removal, AE, fell out

The functional life of the Guardian[™] Sensor (3) will also be characterized. The duration of Guardian[™] Sensor (3) performance from the time of first valid Interstitial Signal (ISIG) to the last glucose reading (i.e., time to end of Guardian[™] Sensor (3) life) will be described with Kaplan-Meier curves.

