7.3 Sensor Disposition

The number of Guardian[™] Sensor (3) insertions and Guardian[™] Sensor (3) removals for every subject enrolled in the study will be presented.

A descriptive analysis of Guardian[™] Sensor (3) disposition including Guardian[™] Sensor (3) dislodgement and reasons why it dislodged will be included in the Final Report. Guardian[™] Sensor (3) insertion and removals will be characterized by the following:

- Duration of Guardian[™] Sensor (3) wear by investigational center subject report
- The number and percentage of Guardian™ Sensor (3)s remaining in place at study end
- Reason for removal: for example, scheduled removal, companion sensor removal, early removal

Version: V1.0

The functional life of the primary Guardian[™] Sensor (3) will also be characterized. The duration of Guardian[™] Sensor (3) performance from the time of first valid Interstitial Signal (ISIG) to the time of

last available sensor value will be summarized by descriptive statistics (mean, standard deviation, minimum, median, and maximum) and described with Kaplan-Meier curves as well.

For the duration of GuardianTM Sensor analysis, both the physical sensor life time and functional sensor life time based on sensor level will be provided. The corresponding calculation methods are as following:

- (1) Physical sensor life time (hours) = (Removal time-Insertion time) /3600, the insertion time and removal time collected in OC-RDC database.
- (2) Functional sensor life time (hours): The analysis data collected in Guardian™ Sensor external database. Related calculation method is as following:
- 1) Find the first valid Interstitial Signal (ISIG) value (i.e. first ISIG after connection indicator), and its corresponding time will be considered as beginning time.
 - 2) Find the last available Sensor value, and its corresponding time will be considered as ending time.
 - 3) Functional sensor life time (hours) = (Ending time- Beginning time) /3600.

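### A mild, non-infectious skin reaction that ends sensor wear early is not reported as an adverse event, and no output described in the plan identifies it as the cause of removal

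*Protocol*

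**What the plan says.** **Removal.** Protocol 11.7 states: "Either subject or investigational center may remove a sensor if they are concerned with skin irritation or skin discomfort". No grade is required. The risk table in Protocol 10.1 adds: "If a sensor site becomes infected or inflamed, the sensor should be removed and another placed in a new location".

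**AE reporting.** Protocol 11.7 restricts the AE form: "An AE eCRF will only be completed if the skin assessment observation meets the following criteria". Two criteria follow. One is infection. The other is "Any observation that meets the criteria of moderate or severe per the skin assessment case report form", illustrated by a bruise of at least 6 cm and a rash needing prescription treatment. Worsening after the assessment is to be considered for AE reporting.

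**Recording of mild findings.** Of the mild irritation, redness, bleeding or bruising that is expected, 11.7 says: "These events are to be documented and captured on the Skin Assessment eCRF". It also says: "The Investigational Center staff will complete a skin assessment each time a study sensor is removed from a subject", however long the sensor was in and however long ago it came out. Protocol 14.11 and SAP 7.9 both list skin assessment of insertion sites among the safety items to be summarised.

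**Removal reasons.** Protocol 14.3 has "Reason for removal: for example, scheduled removal, AE, fell out". SAP 7.3 has "Reason for removal: for example, scheduled removal, companion sensor removal, early removal". Under Protocol 9.2.4.3, subjects are reminded to note when and why any sensor came off early.

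**The concern.** Part of the study's primary purpose is to show safety over 170 hours of wear. How often a skin reaction stops someone completing that wear is a direct tolerability result for the claim. The AE rule in 11.7 depends on infection and grade, with examples based on size and treatment. It takes no account of whether the reaction ended wear. The general AE definition in Protocol 11.1 has no severity threshold, and 11.2 asks the investigator to record all AEs, so 11.7 is narrower than the sections around it.

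The timing of the assessment adds to this. A sensor removed at home may be assessed days later, when the reaction has faded, and the grade given then decides whether an AE form is completed.

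What is at stake is the device-related AE count, which would omit these cases, and the reader's ability to count sensors stopped because of the skin.

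**Working it through.** No figure in the plan needs reproducing. The check follows three kinds of early removal through the outputs that the text describes.

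| Case | AE table | Skin-assessment summary | Sensor disposition |
|---|---|---|---|
| Infection, or moderate/severe reaction, sensor removed early | Yes, by 11.7 | Yes | Counted; the SAP examples do not name AE as a reason |
| Mild, non-infectious reaction, sensor removed early | No, unless it later worsens and is judged reportable | Yes, as a mild finding | Counted; the SAP examples do not name a skin reason |
| Mild, non-infectious reaction, sensor worn to schedule | No, with the same exception | Yes, as a mild finding | Scheduled removal |

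Rows two and three differ only in the last column. The skin summary is not described as split by removal reason or timing, and the disposition table is not described as split by skin finding. From the outputs as described, a reader cannot tell how many mild reactions ended wear.

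**Does another record supply the link?**

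- *Deviations.* Protocol 9.12.1.1 assigns a sensor-wear deviation only when the site tells the subject to remove the sensor before Day 7. A subject's own decision to remove it for irritation leaves no deviation.
- *The AE reason in Protocol 14.3.* It would not clearly have caught the mild case either, because under 11.7 that case has no AE form to match.
- *Worsening.* A reaction that ended wear need not worsen once the sensor is off.
- *Subject's note of early removal (9.2.4.3).* The reason is meant to be collected, so the raw material should exist. The text does not say how it will be tabulated.

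**Size.** The documents give no rate of early removal for mild reactions. Purely as an illustration:

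- 72 subjects × 2 sensors = 144 sensors before replacements. This is an upper figure, because enrolment is counted from consent and the 72 can include screen failures.
- Assume 2% to 5% are removed early for a mild reaction: 0.02 × 144 = 2.9 and 0.05 × 144 = 7.2, or about 3 to 7 sensors.
- If each is in a different subject: 3/72 = 4.2% to 7/72 = 9.7% of subjects.
- If there were no other device-related AE, the table would read 0 of 72, with exact two-sided 95% upper limit 1 − 0.025^(1/72) = 4.99%.

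The 2% to 5% is an assumption with no source in the documents. The example shows only that a handful of such removals would matter to a table of this size.

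**The case against.** The strongest defence is that the data are not lost. Expected mild reactions have their own form, completed at every removal, and their own place in the safety summary. Keeping them off the AE form is a stated design choice. This stands, and it limits the point to reporting.

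A reader might go further and infer four things that the documents do not support.

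- *That such reactions appear in no table.* They reach the skin-assessment summary, and the removal is counted in sensor disposition. Only the link is missing.
- *That a site reaction of this kind can never become an AE.* Infection qualifies whatever its grade, and worsening must be considered for reporting.
- *That the SAP has deleted AE as a removal reason.* Both lists are introduced as examples, and the table shells are in an appendix that was not available. What can be said is that the SAP's examples name neither AE nor skin reaction, and that SAP 7.13 does not mention the difference from the protocol.
- *That skin removals are pooled with sensors that fell out.* SAP 7.3 separately promises an analysis of dislodgement and its reasons, so pooling is not established.

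It is also fair to object that the moderate and severe criteria are on a form that was not available. If that form already grades a wear-ending reaction as moderate, 11.7 needs no change.

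**Conclusion.** The point holds for mild, non-infectious insertion-site or adhesive reactions that lead to removal before the scheduled time. The wording of 11.7 keeps these off the AE form, and no output described in the protocol or SAP identifies them as the reason wear ended. Reactions that are infected or graded moderate or severe are not affected by the AE gap.

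The conclusion rests on two assumptions: that the skin grading form does not itself treat early removal as moderate, and that the table shells do not already show a skin-related removal reason. How many sensors are involved is unknown. The primary accuracy endpoints and the success rule are untouched. Priority: minor.

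**What to change.** 1. **Protocol 11.7.** Add a third AE-reporting criterion: any insertion-site or adhesive observation that led to removal of a sensor before its scheduled time, whatever its grade. This is not needed if the skin form already grades such observations as moderate; in that case, say so in 11.7.
2. **SAP 7.3.** Report *skin reaction/discomfort* and *AE* as separate early-removal reasons. Cross-tabulate removal reason by skin-assessment grade, and check the skin-related removals against the AE listing.

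The removal reason and the skin assessment are already due to be collected, so no visit or procedure is added. The cost is one line in each document, a few extra AE forms and a slightly higher device-related AE count. The change concerns reporting only and leaves the decision to remove a sensor as it is.

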14.1. General Considerations

All data collected from the time of screening until the end of the study will be collected either on eCRFs or electronically by downloading the various devices. Data and analysis will be summarized in a Clinical Study Report.

14.2. Subject Disposition

The number of subjects enrolled in the study will be presented. The reasons for discontinuing prior to study completion will be summarized.

10768467DOC Version C

14.3. Sensor Disposition

The number of Guardian[™] Sensor (3) insertions and Guardian[™] Sensor (3) removals for every subject enrolled in the study will be presented.

A descriptive analysis of Guardian[™] Sensor (3) disposition including Guardian[™] Sensor (3) dislodgement and reasons why it dislodged will be included in the Final Report. Guardian[™] Sensor (3) insertion and removals will be characterized by the following:

- Duration of Guardian™ Sensor (3) wear by investigational center subject report
- The number and percentage of Guardian™ Sensor (3)s remaining in place at study end
- Reason for removal: for example, scheduled removal, AE, fell out

The functional life of the Guardian[™] Sensor (3) will also be characterized. The duration of Guardian[™] Sensor (3) performance from the time of first valid Interstitial Signal (ISIG) to the last glucose reading (i.e., time to end of Guardian[™] Sensor (3) life) will be described with Kaplan-Meier curves.

